3.5.3.1.2 Pediatric Population

There will be no efficacy assessment of durability of long-term SVR in this population as enrollment in this study will be limited to pediatric subjects who were virologic failures and had emergent RAS present at FW12 in the prior treatment study.

In pediatric subjects, HCV sequence analysis will be performed to evaluate the presence of RASs and the persistence of RASs over time.

3.5.3.2 Safety Endpoints

3.5.3.2.1 Adult Population

Safety and signs of disease progression are assessed for all adult subjects by physical examination, drug-related SAEs, ECIs, any AEs related to protocol-specified procedures (blood draw), and laboratory tests.

3.5.3.2.2 Pediatric Population

The safety analyses will be based on data from all pediatric subjects entering the study. Long-term safety assessments include any AEs related to protocol-specified procedures (blood draw) and drug-related SAEs.

3.5.4 Analysis Populations

3.5.4.1 Efficacy Analysis and RAS Populations

3.5.4.1.1 Adult Population

The analysis population for the time to relapse analysis will be all adult subjects who achieved SVR and were not a virologic failure in the prior treatment study nor received a new HCV therapy after completing treatment with a GZR containing regimen in the prior treatment study.

HCV sequence substitutions will be evaluated in adult subjects who sign an informed consent for this study and have HCV RNA ≥ 1000 IU/mL at study entry and/or at any visit during the study period.

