1.3.1 Durability of Virologic Response

At the time of PN017 initiation, FDA guidance for industry specified that HCV-infected patients treated with a DAA and achieving sustained viral response (SVR) be followed for at least 3 years to ensure durability of response. As the field of HCV therapies advanced, data accrued demonstrated that SVR observed at 12 and 24 weeks after DAA treatment was durable for years [2][3]. These findings resulted in modifications to the regulatory guidance to no longer assess durability of response beyond 24 weeks of follow-up [4]. Subjects who achieved SVR in a prior treatment study and were enrolled into PN017 were subsequently discontinued at their next visit due to amendment (AM) 03. All subjects up to discontinuation or study completion will be included in data analyses of durability of response.

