2.7 STATISTICAL ANALYSIS PLAN SUMMARY

Key elements of the statistical analysis plan (SAP) are summarized below; the comprehensive plan is provided in Section 3.5. The adult population and pediatric population will be summarized separately.

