2.7.1 Efficacy Analyses

2.7.1.1 Adult Population

The primary endpoints, primary analysis population, and statistical methods that will be employed for the efficacy analyses in the adult population are presented in [Table 3](#).

There will be no formal efficacy hypothesis testing conducted in this study.

The primary efficacy objectives of this study are to evaluate the durability of response in subjects who achieved SVR in the prior treatment study, as follows, and the evaluation of antiviral resistance to GZR, as described in 2.7.3.

Durability of SVR will primarily be evaluated based upon the time to viral relapse, which is defined as the time from last dose of study therapy taken in the prior treatment study until the date where HCV RNA is \geq LLoQ (see Section 2.5). The analysis population for the time to relapse analysis will be all subjects who achieved SVR during the follow-up

period of the prior treatment study and did not start any new HCV therapy between the end of the prior treatment study and entry in this study.

The distribution of time to viral relapse will be summarized using Kaplan-Meier estimates. In addition, the percentage of subjects who remain HCV RNA <LLoQ during the course of this study will be summarized.

Subjects who receive other treatments for HCV concurrently with this protocol or prior to PN017 and after completion of therapy in the prior treatment study will be discontinued from PN017, and their data excluded from analysis from the time of initiation of new therapy.

Table 3

Summary of Analysis Strategy for Key Efficacy Endpoints
(Adult Population)

Endpoint/Variable	Statistical Method	Analysis Population	Missing Data Approach
Primary:			
Durability of SVR (Time to viral relapse)	Kaplan-Meier plot and summary statistics	All adult subjects entered who achieved SVR in the prior treatment study and who did not start new HCV treatment between end of the prior treatment study and study entry in PN017.	Data as Observed ^a
Antiviral resistance	Descriptive statistics	RAS Analysis Population is defined as allocated adult subjects who met Virologic Failure criteria in the prior treatment study or up to entry into PN017 and who entered PN017 with TD(q) HCV RNA, excluding subjects who were reinfected or who meet any of the following criteria: Failure to receive at least 1 dose of GZR in the prior treatment study or subject had another protocol violation.	Data as Observed

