3.2.2 Concomitant Medication(s)/Treatment(s)

3.2.2.1 Adult Population

In the original protocol, subjects were permitted to participate in other treatment studies for HCV concurrently with this protocol.

Starting with AM 03, subjects are not permitted to receive any therapies used for the treatment of HCV concurrently with this protocol.

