3.5.5 Statistical Methods

No hypothesis testing will be performed in this non-drug long-term follow-up study. Efficacy and safety data will be summarized using descriptive statistics. As subjects are permitted to participate in other treatment studies for HCV concurrently with this protocol, all follow-up data collected after subjects started HCV treatment will be summarized separately.

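### The time-to-relapse population for primary objective 1 is stated inconsistently: the new-therapy exclusion in 3.5.4.1.1 has no end date, and the entry HCV RNA condition does not fit the pre-entry relapse rule in 3.5.5.1.1

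*Combined protocol and SAP*

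**What the plan says.** **New HCV therapy.** Section 2.7 presents itself as a summary and says that "the comprehensive plan is provided in Section 3.5". Within Section 3.5, the population paragraph (3.5.4.1.1) takes adults who achieved SVR and were not prior-study virologic failures, "nor received a new HCV therapy after completing treatment with a GZR containing regimen in the prior treatment study". It names no date at which that exclusion stops.

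The summary does name one. The text of 2.7.1.1 takes SVR subjects who "did not start any new HCV therapy between the end of the prior treatment study and entry in this study", and Table 3 takes those "who did not start new HCV treatment between end of the prior treatment study and study entry in PN017". For therapy begun later, 2.7.1.1 has subjects discontinued and "their data excluded from analysis from the time of initiation of new therapy". Section 3.5.5 says that "all follow-up data collected after subjects started HCV treatment will be summarized separately". Section 1.3.1 adds: "All subjects up to discontinuation or study completion will be included in data analyses of durability of response".

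Treatment during PN017 was possible. Section 3.2.2.1 records: "In the original protocol, subjects were permitted to participate in other treatment studies for HCV concurrently with this protocol". From AM 03 it leads to discontinuation.

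**HCV RNA at entry.** Objective 1 (2.1.1.1) is limited to subjects below LLoQ at PN017 entry. Section 2.5 sets the same condition for subjects enrolled before AM 03. The population wording in 2.7.1.1, Table 3 and 3.5.4.1.1 does not contain it. Section 3.5.5.1.1 treats a relapse between the end of the prior study and PN017 entry as an event dated at entry. Time runs from the last dose in the prior study (3.5.3.1.1).

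**The concern.** Durability of SVR is the first primary objective, and its Kaplan-Meier estimate depends on which section the programmer follows.

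The open-ended exclusion in 3.5.4.1.1 is the more serious of the two conflicts. Retreatment is a natural consequence of relapse. A rule that removes anyone ever retreated therefore selects on what happens after the event, and it takes out the event and the subject together. The literal rule could be programmed, because 3.3.1.1 collects HCV therapies at every visit. Section 3.5 says that no separate SAP will be issued, so no later document is planned to settle the wording.

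The entry condition raises a different question: whether a relapse found at Visit 1 is an event or lies outside the population. If the condition is applied, the time scale also needs care. Follow-up is counted from the last dose, yet everyone admitted is known to be below LLoQ at Visit 1, so the stretch before Visit 1 cannot contain an event.

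**Working it through.** The plan states no figure to reproduce: no N, relapse count or retreatment share.

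**Step 1: the rules side by side**, for three subjects who all had SVR in the prior study and no new therapy before entry.

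| Subject | 3.5.4.1.1, literally | 2.7.1.1 and Table 3 | Objective 1 and 2.5 |
|---|---|---|---|
| A: below LLoQ at entry, confirmed relapse in PN017, then new therapy | Out; event lost | In; event counted, later data set aside | In |
| B: below LLoQ at entry, reinfected in PN017, then new therapy | Out | In; not a relapse | In |
| C: quantifiable at Visit 1, confirmed, not reinfection | In; event at entry by 3.5.5.1.1 | In; event at entry by 3.5.5.1.1 | Out |

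A and B show the new-therapy conflict. C shows the entry conflict.

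**Step 2: direction of the new-therapy conflict.** Use a simple proportion, which equals 1 minus Kaplan-Meier under complete follow-up. With N subjects, x relapsers, k relapsers later retreated (type A) and m subjects retreated for reinfection (type B), the literal rule turns x/N into (x − k)/(N − k − m). Assume N = 1000 and x = 8:

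- k = 0, m = 0: 8/1000 = 0.80%.
- k = 4, m = 0: 4/996 = 0.40%.
- k = 8, m = 0: 0/992 = 0.00%.
- k = 0, m = 20: 8/980 = 0.82%.

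The two removals cancel when (x − k)/(N − k − m) = x/N, that is, m = k(N − x)/x. Here that is 992/8 = 124 reinfection removals for each relapser lost. So both directions are possible, but one lost relapse outweighs many lost non-events when relapse is rare.

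**Step 3: the entry conflict.** Let p be the number of type C subjects. Without the entry condition the proportion is (x + p)/(N + p); with it, x/N. On the same assumed N and x, 0.80% compares with:

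- p = 1: 9/1001 = 0.90%.
- p = 3: 11/1003 = 1.10%.
- p = 5: 13/1005 = 1.29%.

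**Step 4: event-free time.** FW24 is day 24 × 7 = 168 after the last dose. Taking the 3-month enrollment window as 91 days, Visit 1 falls as late as day 168 + 91 = 259. For subjects enrolled before AM 03, 3.5.5.1.1 allows screening up to one year from last dose, which is up to 365 − 168 = 197 days after FW24. If the entry condition is applied with time from last dose and no delayed entry, that stretch is counted at risk but is event-free by construction. Delayed entry by the Table 7 intervals would not help under the 3-month window, because day 259 still lies in the Month 6 interval (days 1 to 274). Exact days are needed.

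**The case against.** The best defence is that the documents largely show what 3.5.4.1.1 means. The rest of its sentence describes status in the prior study. The summary text and Table 3 both bound the window, and exclusion criterion 2 in section 2.3 uses the same one. The rule that later data are summarized separately sits in 3.5.5, inside the comprehensive plan, and would have little to act on in the durability analysis if retreated subjects were already gone. This makes the baseline reading plausible and probably intended. It does not put the end date into the paragraph that defines the population.

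On the entry condition, durability among subjects still below LLoQ at entry is a legitimate target. Pre-entry relapsers would not vanish from the report: Table 3's RAS population takes subjects who met failure criteria up to PN017 entry and entered with quantifiable RNA, excluding reinfection, although it pools them with prior-study failures. Section 3.5.5.4 also tabulates baseline characteristics by quantifiable or below-LLoQ RNA at entry. These soften the loss but do not say whether subject C is an event.

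AM 03 also limits the exposure, because it discontinued retreated subjects and, outside PN052, those who entered below LLoQ. It does not remove it. Retreatment was allowed earlier, those subjects' data stay in the durability analysis, and PN052 subjects with SVR remain in follow-up.

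**Conclusion.** Both inconsistencies stand on the current text. The first is a missing end date in 3.5.4.1.1 which, followed literally, understates late relapse to the extent that relapsers are among those retreated. The second is an entry condition in objective 1 and 2.5 that does not fit the pre-entry relapse rule in 3.5.5.1.1. The size of either effect cannot be determined from the documents; every N and event count used above is an assumption. The study tests no hypothesis and fixes no sample size, so the point ranks between minor and should-fix.

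Four stronger readings are tempting but not supported:

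- That the error can only flatter durability. The literal rule also removes subjects retreated for reinfection, who are non-events, and that slightly raises the estimate.
- That section 2.5 sets up a rival population by assessing late relapse at the entry visit. That sentence concerns subjects who entered TND or TD(u), so it shares the entry condition.
- That a pre-entry relapser can never meet the entry condition. Section 3.5.5.4 substitutes a recent prior-study value when Visit 1 RNA is missing, which leaves a narrow overlap. The conflict is for subjects measured at or above LLoQ at Visit 1.
- That the effect is known to be important. Calculations on assumed risks show direction and mechanism only.

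**What to change.** **New therapy.** In 3.5.4.1.1, limit the exclusion to new HCV therapy started between the end of the prior treatment study and PN017 entry, as Table 3 already does. For therapy started later, keep the subject in the population, count a confirmed, non-reinfection relapse that precedes the therapy as an event, and otherwise censor at the last HCV RNA before the therapy.

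**Entry condition.** Reconcile 2.1.1.1 and 2.5 with 3.5.5.1.1 by one of two routes:

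- Use the Table 3 population without the entry condition and keep the pre-entry relapse rule. This changes the wording of objective 1 and 2.5.
- Keep the entry condition and delete the pre-entry relapse rule. Carry the condition into 2.7.1.1, Table 3 and 3.5.4.1.1, use delayed entry at Visit 1 on exact days, and report how many prior-study SVR subjects had confirmed, non-reinfection quantifiable RNA at entry. This changes only the analysis text.

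**Cost.** No new data are needed. The first change is one clause and a short handling rule. By the plan's own rule in Section 3.5, a change to a primary objective or its methods after the study has begun goes through a protocol amendment.

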2.1.1.1	Adult Population (subsection of Primary Objectives and Hypotheses)	
Primary Objective #2:
 
• Original wording: To evaluate the presence of antiviral resistance, NS3/4A, NS5A and/or NS5B, (as appropriate) and determine if there is a reversion to a wild-type pattern within the 3 years (all protocols except PN 052) or 5 years timeframe for PN 052 of this long-term follow-up study.
○ Subjects enrolling in PN 017 with quantifiable HCV RNA after having failed therapy will be followed for 3 years (all studies except PN 052) or 5 years (PN 052)• Amendment 04 wording: To evaluate the presence of treatment-emergent antiviral resistance to NS3/4A, NS5A and/or NS5B regions, (as applicable) and determine if there is a reversion to wild-type pattern within the 3-year time frame of this long-term follow-up study (or 5-year time frame for subjects from PN052) in subjects with virologic failure in the prior treatment study and with HCV RNA ≥ 1000 IU/mL in Protocol 017.	
The new wording of this objective reflects the current interest in the focus on treatment-emergent RASs and the persistence of these RASs. Additionally, wording was added to align with Merck's standard methodology for resistance testing (ie, resistance can only be assessed in subjects when HCV RNA levels are >1000 IU/mL).
 
Sub-bullet text was deleted because it is found in other sections of the protocol.

Section Number(s)	Section Title(s)	Description of Change(s)	Rationale

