2. CORE PROTOCOL

2.1 OBJECTIVES AND HYPOTHESES

2.1.1 Primary

2.1.1.1 Adult Population

In HCV-infected subjects who received at least 1 dose of GZR in a previous study:

1. **Objective:** To evaluate the durability of response in subjects who achieved SVR₂₄ in the prior treatment study and at the time of entry into PN017 were HCV ribonucleic acid (RNA) <lower limit of quantification (LLoQ) (either target not detected [TND] or target detected, unquantifiable [TD(u)]).
2. **Objective:** To evaluate the presence of treatment-emergent antiviral resistance to NS3/4A, NS5A and/or NS5B regions, (as applicable) and determine if there is a reversion to wild-type pattern within the 3-year time frame of this long-term follow-up study (or 5-year time frame for subjects from PN052) in subjects with virologic failure in the prior treatment study and with HCV RNA ≥ 1000 IU/mL in Protocol 017.
3. **Objective:** To evaluate the long-term safety.

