2.5 LIST OF EFFICACY/PHARMACOKINETIC/IMMUNOGENICITY MEASUREMENTS

The following measurements are applicable for the adult and pediatric populations.

HCV Genotype

Samples will be genotyped using the Food and Drug Administration (FDA) approved Abbott HCV Real Time Genotype II assay which detects HCV GT1a, 1b, 2, 3, 4, 5, and 6 through the use of genotype-specific fluorescent-labeled oligonucleotide probes in a real-time reverse transcriptase-polymerase chain reaction (RT-PCR) assay. The RT-PCR reaction uses 3 sets of HCV specific amplification primers targeting the conserved 5' untranslated region (for all genotypes) and NS5B regions from GT1a and 1b. The assay has accuracy of >96% for GT1, 1a, 1b, 2, 3 and 4, 89% for GT5 and 83% for GT6 with 100% specificity in HCV serologically negative plasma samples. Phylogenetic analyses will be performed using sequences for NS3/4A, NS5A and NS5B to ensure accurate assignment of sample genotype/subtype.

HCV RNA

HCV RNA in plasma will be measured using a COBASTTM AmpliPrep/COBASTTM TaqmanTM HCV Test, v2.0 ® assay with a LLoQ of 15 IU/mL. HCV RNA definitions are presented in [Table 1](#).

Table 1

HCV RNA Definitions

Abbreviation	Definition	HCV RNA Level
TND	Target not detected	HCV RNA not detected
TD(u)	Target detected, unquantifiable	HCV RNA < LLoQ
TD(q)	Target detected, quantifiable	HCV RNA ≥ LLoQ

HCV=hepatitis C virus; LLoQ=lower limit of quantification; RNA=ribonucleic acid

For subjects enrolled prior to AM 03, durability of virologic response will be assessed in all subjects who are HCV RNA <LLoQ (either TND or TD[u]) on Day 1 of entry into this protocol and excluding any subject who is TND/TD(u) due to having received an anti-viral treatment after having failed previous therapy in the parent study.

Failure of therapy due to relapse more than 24 weeks after the end of therapy (termed late relapse) in this group of subjects will be measured as an HCV RNA that is confirmed to be ≥LLoQ and is not due to a new infection or re-infection. Confirmation is defined as an HCV RNA that is target detected, quantifiable (TD[q]) from a separate blood draw repeated in approximately 4 weeks.

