2.7.3 Analysis of Resistant Associated Substitutions

2.7.3.1 Adult Population

The evaluation of antiviral resistance to GZR will be obtained on subject samples with HCV RNA \geq 1000 IU/mL at study entry or during the course of this study; the presence of RASs and the persistence of RASs over time will be summarized using descriptive statistics, with subgroup analyses by class of regimen (e.g. NS3/4A inhibitors, NS5A inhibitors and NS5B inhibitors) as well as by specific components (Table 3). Only subjects who experienced virologic failure (other than reinfection) will be included in these analyses.

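### The adult resistance analysis does not match primary objective 2: three passages select different subjects, and no adult endpoint or method passage limits the summaries to treatment-emergent substitutions

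*Combined protocol and SAP*

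**What the plan says.** Section 2.1.1.1, objective 2, sets the target: "To evaluate the presence of treatment-emergent antiviral resistance to NS3/4A, NS5A and/or NS5B regions" and whether there is reversion to wild type, "in subjects with virologic failure in the prior treatment study and with HCV RNA" of at least 1000 IU/mL in PN017. The lead-in to the adult objectives requires at least one dose of grazoprevir (GZR).

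Four places in the analysis text then say who and what is analysed:

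- **Section 3.5.4.1.1**, under the heading for efficacy and RAS analysis populations: "HCV sequence substitutions will be evaluated in adult subjects who sign an informed consent for this study and have HCV RNA" of at least 1000 IU/mL at entry or any visit. Section 3.5.3.1.1 repeats the RNA condition and names the endpoint as presence and persistence of RASs.
- **Table 3 (Section 2.7.1.1)** defines a RAS Analysis Population: failure in the prior study or by PN017 entry, with quantifiable RNA at entry. It excludes reinfected subjects and adds: "Failure to receive at least 1 dose of GZR in the prior treatment study or subject had another protocol violation".
- **Section 2.7.3.1** uses samples of at least 1000 IU/mL at entry or later, cites Table 3, and adds: "Only subjects who experienced virologic failure (other than reinfection) will be included in these analyses".
- **Section 3.5.5.3.1** summarises sequence substitutions descriptively and allows a Kaplan-Meier estimate of the return of individual resistance mutations to wild type.

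Section 2.7 calls Section 3.5 the comprehensive plan, and Section 3.5 says no separate SAP will be issued.

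**The concern.** Objective 2 is primary, and its result depends on which passage the programmer follows. Two faults are separate and can act together.

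First, the denominator. The three population statements differ from one another, and none equals objective 2.

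Second, the substitutions counted. Objective 2 is limited to treatment-emergent resistance; the adult endpoint and method passages are not. A polymorphism already present before treatment also differs from wild type, so speaking of return to wild type does not supply the missing limit. The pediatric Table 4 does name treatment-emergent RASs in its population, so the adult silence is a real difference in the text. The amendment rationale points the same way, "The new wording of this objective reflects the current interest in the focus on treatment-emergent RASs and the persistence of these RASs", but it is cited only for intent; the current wording of Section 2.1.1.1 carries the point alone.

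**Working it through.** The plan gives no figure to reproduce, and the sample size is not pre-set (Section 3.5.7). The check is a comparison of the rules, followed by the algebra of direction.

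**Rules side by side**

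| Rule | Failure condition | RNA condition | Reinfection | Treatment-emergent limit |
|---|---|---|---|---|
| Objective 2 | In the prior study | At least 1000 IU/mL in PN017 | Not mentioned | Yes |
| 3.5.4.1.1 (with 3.5.3.1.1) | None | At least 1000 IU/mL at entry or any visit | Not mentioned | No |
| Table 3 | In the prior study or by entry | Quantifiable at entry (LLoQ 15 IU/mL, Section 2.5) | Excluded | No |
| 2.7.3.1 | Yes, timing not stated | Samples of at least 1000 IU/mL, at entry or later | Not counted as failure | No |

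**Subjects on whom the rules part**

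- *Prior SVR, late relapse reaching 1000 IU/mL.* Sequenced under footnote 5 of the adult flow chart. Outside objective 2 and Table 3; inside 3.5.4.1.1. Section 2.7.3.1 can be read either way, because Section 2.5 describes late relapse as a failure of therapy.
- *Prior SVR, reinfected during PN017, at least 1000 IU/mL.* Admitted only by 3.5.4.1.1.
- *Relapse between the prior study and entry, at least 1000 IU/mL.* Outside objective 2; admitted by the other three.
- *Prior failure, below LLoQ at entry, later at least 1000 IU/mL.* Inside objective 2, 3.5.4.1.1 and the wording of 2.7.3.1; dropped by Table 3.
- *Prior failure with some other protocol violation.* Dropped only by Table 3, which does not list the violations.
- *Prior failure, 15 to 999 IU/mL throughout.* Admitted only by Table 3, and only to the denominator, since no sample qualifies for sequencing.

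**Direction, persistence and reversion.** For one mutation, let n_e carriers be treatment-emergent with reversion R_e, and n_p carriers pre-existing with reversion R_p. Pooled reversion = (n_e·R_e + n_p·R_p)/(n_e + n_p). This is below R_e whenever n_p > 0 and R_p < R_e, and equals R_e when n_p = 0. That pre-existing variants revert less often is an assumption; the documents do not state it.

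**Direction, presence.** Let p be the share of prior failures with a treatment-emergent RAS, a the share with only a pre-existing RAS, k the extra subjects admitted per failure, and r the share of those extras with any RAS. Reported presence = (p + a + k·r)/(1 + k). It exceeds p if a > k(p − r) and falls below p if a < k(p − r). The documents give none of p, a, k or r, so neither sign nor size can be fixed.

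**The case against.** **Section 3.5.4.1.1 may be only a sequencing rule.** It resembles the testing rules in the flow chart and in Sections 2.5 and 3.3.1.1. But it stands under analysis populations in the comprehensive plan, and sequencing is already covered in those other places. The reading fails on the heading.

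**Section 2.7.3.1 cites Table 3, so the two may be read together**, one choosing subjects and the other samples. This is fair. It takes late relapsers out of Section 2.7 and makes subjects who never reach 1000 IU/mL a denominator matter only. It still leaves Table 3 at odds with objective 2 on failures arising up to entry, the quantifiable-at-entry condition and the protocol-violation exclusion, and at odds with 3.5.4.1.1.

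**Section 3.5.2 points back to the objectives.** It is a pointer only; it sets no population and does not define treatment-emergent.

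**Reach is limited.** This stands. From amendment 03, new adult enrollment was limited to failures, failures due to reinfection and retreated failures were excluded, and subjects outside PN052 who entered below LLoQ were discontinued. Late relapse, in-study reinfection and failures below LLoQ at entry are probably uncommon. They remain possible for subjects enrolled before amendment 03 and for PN052 subjects with SVR who stayed in follow-up.

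**The study is descriptive and the Kaplan-Meier analysis optional.** True, and it limits the consequence. Descriptive summaries of a primary objective still need one denominator.

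A reader might also infer that objective 2 itself excludes reinfection. It does not; that exclusion comes from Table 3 and Section 2.7.3.1.

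**Conclusion.** The concern holds. As written, Sections 3.5.4.1.1, 3.5.3.1.1 and 3.5.5.3.1 would bring prior-SVR late relapsers, in-study reinfections and pre-existing substitutions into the report on objective 2, which covers none of these three. Table 3 and Section 2.7.3.1 do not repair this, since each differs from the objective in its own way and neither carries the treatment-emergent limit.

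The size is unknown. For mutations that also occur before treatment, persistence would be overstated and any Kaplan-Meier reversion understated, assuming pre-existing variants revert less often. Mutations that never occur before treatment are unaffected by this second fault. The net direction for RAS presence is uncertain.

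A reader might infer a large or calculable bias, or a firm count of subject types on which each passage departs from the objective. The documents support neither. They give no shares for any subject type or for pre-existing RASs, and a count would turn on optional readings: whether late relapse is virologic failure in Section 2.7.3.1, and how silence about reinfection is scored.

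**What to change.** By protocol amendment, which Section 3.5 requires for methods tied to a primary objective:

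1. Use one adult RAS population in Table 3, Section 2.7.3.1 and Section 3.5.4.1.1, and align Section 3.5.3.1.1. As in objective 2: at least one dose of GZR, virologic failure in the prior study, and at least one PN017 sample of 1000 IU/mL or more. Keep the reinfection exclusion already in Table 3 and Section 2.7.3.1, and say that it applies to reinfection during PN017.
2. State whether failures arising after the prior study but by entry are kept, and whether the exclusion for other protocol violations is kept. If it is, list the violations.
3. In Sections 3.5.3.1.1 and 3.5.5.3.1, limit the main presence, persistence and any Kaplan-Meier reversion summaries to treatment-emergent substitutions. Define these against the prior-study pre-treatment sequence, for example absent before treatment and present at failure, or use the prior studies' own definition if they have one.
4. Report separately: pre-existing RASs, subjects or gene regions without a baseline sequence, and late relapsers.

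Cost: the amendment, a programming flag, and some work to align baseline sequences across the prior studies, which number more than 20 and used several regimens (Section 1.3). Section 3.2.4.1 already provides for transfer of all prior-study sequence analysis, so no new sampling is needed. It does not say that every subject and region has a baseline sequence. The main table will hold fewer substitutions.
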